4.4 Sample size calculation

Our sample size is based on an cumulative live birth rate. We anticipate an 18% pregnancy rate after 3 cycles natural cycle IUI. We presume that the clinical relevant difference is 8%. To test the hypothesis that IUI with letrozole increased the pregnancy rate to 26% as compared to natural cycle IUI, we need to include 483 women per arm (total 966). (two sided-test, alpha .05, beta .80, 15% loss to follow-up). Firstly we will collect 100 women for a pilot study.

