8. STATISTICAL ANALYSIS

Step 1: Summarizing trial data.

Baseline data and outcome data will be separately summarized. For continuous variables, we will examine the distribution of the observations, and if normally distributed then we will summarize them as means with standard deviations (SDs). If they are not normally distributed, then medians and inter-quartile ranges (IRQs) will be reported. For dichotomous data, we will provide proportions (or percentages). In addition to the baseline and outcome data, we will also summarize the recruitment numbers, those lost to follow-up, protocol violations and other relevant data.

Step 2: Inter-group comparisons.

The analysis of all outcomes will be done on an intention to treat basis.

The effectiveness of IUI with letrozole versus IUI in natural cycle will be expressed as a rate ratio for live birth with corresponding 95% confidence intervals. A formal test of the difference in rate will be performed using chi-square test statistics. The effectiveness over time will be evaluated in life tables and differences in live birth over time will be evaluated using the log-rank test. Further dichotomous outcomes will be analyzed using either Fishers Exact Test or chi-square as appropriate. For continuous outcomes we will use t-test if the observations in each trial arm are normally distributed, and if non-normally distributed, then Mann-Whitney-U test will be employed. Although p-values will be reported, the focus will be on providing 95% confidence intervals around point estimates as these are more useful in interpreting the findings of the trial.

Step 3: Adjustments and sensitivity analyses.

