If randomization fails to achieve balanced groups, then we will perform secondary analyses in which we will adjust for unbalanced prognostic factors using procedures such as logistic regression. If the primary unadjusted analysis and secondary adjusted analysis are discordant, we will give greater weighting to the primary analysis in the interpretation of trial findings. For issues such losses to follow-up, missing data, and protocol violations, we will attempt sensitivity ("worst-case scenario") analyses to explore the effect of these factors on the trial findings. As a secondary analysis, we will adjust for missing data using imputation techniques to explore the effects of such imputations on the trial findings. The effect of baseline characteristics on the primary outcome will be explored using logistic regression analysis. In sub analyses the association between follicular growth and live birth will be evaluated.

Details of the analysis will be described in a separate statistical analysis plan, that will be developed during the study, and finalized before data lock.

Interim Analysis

Interim analysis will be done after completion data recruitment of the first 50 participants. An independent Data Safety Monitoring Committee (DSMC) will be invited. The DSMC will be asked to assess the endpoint ongoing pregnancy, as data on live birth will not be available. Also, the DSMC will be provided insight in the SAE's that have occurred. The continuation of the study will depend on the advice of DSMC. A formal stopping rule will be formulated in the separate statistical analysis plan.

Economic evaluation

An economic analysis will be performed alongside the clinical trial. The economic analysis will be performed from a healthcare perspective. Depending on the outcome of live birth rates in both groups, the economic analysis will be a cost-minimization of cost-effectiveness analysis.

Cost-effectiveness of each strategy will be presented as cost per live birth and costs

pre clinical pregnancy. Robustness of the results for various assumptions and parameter estimates will be explored in sensitivity analysis outcomes and will be expressed in ICER graphs and cost-effectiveness acceptability curves. A decision model will be used to evaluate the optimal strategy.

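### The worst-case sensitivity analysis has no scoring rule for missing live births; at or near the planned loss and effect, the extreme bound alone cannot tell a robust result from a fragile one

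*Combined protocol and SAP*

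**What the plan says.** Section 8, Step 3, deals with incomplete data in two sentences. The first is "For issues such losses to follow-up, missing data, and protocol violations, we will attempt sensitivity ('worst-case scenario') analyses". The second adds imputation as a secondary analysis and gives no method, assumption or range. Neither sentence states which outcome is assigned to a woman whose live-birth status is unknown, or what would count as a robust result. The same section defers analysis details to a separate statistical analysis plan, to be written during the study and finalised before data lock.

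Step 2 of section 8 sets the analysis principle: "The analysis of all outcomes will be done on an intention to treat basis". The effect measure is a rate ratio for live birth with a 95% confidence interval, tested by chi-square.

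Section 4.4 supplies the planning figures: "We anticipate an 18% pregnancy rate after 3 cycles natural cycle IUI", a rise to 26% with letrozole, and "we need to include 483 women per arm (total 966"), with these settings: "two sided-test, alpha .05, beta .80, 15% loss to follow-up".

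**The concern.** A sensitivity analysis for missing outcomes should tell the reader how far the lost women would have to differ from the observed women before the conclusion changes. A single extreme scenario does this only when the loss is small relative to the effect. Here the plan allows for 15% loss against an effect of 8 percentage points. In a two-arm comparison, worst case usually means that lost women on the new treatment fail and lost controls succeed. With 15% lost per arm, that assumption takes away more than the planned effect.

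Because no scoring rule is written down, the choice among quite different rules stays open while an open-label trial is running. The sentence also applies the same label to protocol violations, where the outcome is often known. Read literally, that could clash with intention to treat. What is at stake is how readers judge the robustness of the primary result, not the primary result itself.

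**Working it through.** **Inputs.** From section 4.4: 18% natural cycle, 26% letrozole, 483 per arm, two-sided alpha 0.05, power 80% (printed as beta), 15% loss. From section 8: chi-square test and rate ratio (RR) with 95% CI. Assumptions of this check: the 18% and 26% are live-birth rates, loss is equal in both arms, and the observed rates equal the planned ones.

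**1. The plan's own figure.** With pooled variance and mean rate 0.22:

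n = [1.96 × √(2 × 0.22 × 0.78) + 0.84 × √(0.18 × 0.82 + 0.26 × 0.74)]² / 0.08² = 420 per arm (rounded up).

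420 × 1.15 = 483, which matches section 4.4.

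**2. A trial that goes to plan.** 483 × 0.15 ≈ 72 lost and 411 observed per arm. 0.26 × 411 ≈ 107 and 0.18 × 411 ≈ 74 live births.

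**3. Scoring rules compared.**

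| Rule for lost women | Letrozole | Natural cycle | RR | p |
|---|---|---|---|---|
| Observed cases only | 107/411 = 26.0% | 74/411 = 18.0% | 1.45 (95% CI 1.11 to 1.88) | 0.0055 |
| Letrozole no birth, natural cycle birth | 107/483 = 22.2% | (74 + 72)/483 = 30.2% | 0.73 (0.59 to 0.91) | 0.004, reversed |
| No birth in both arms | 107/483 = 22.2% | 74/483 = 15.3% | 1.45 (1.11 to 1.89) | 0.0065 |
| Birth in both arms | 179/483 = 37.1% | 146/483 = 30.2% | 1.23 | 0.025 |
| Letrozole birth, natural cycle no birth (best case) | 179/483 = 37.1% | 74/483 = 15.3% | 2.42 | not needed here |

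**4. Dependence on the loss.** With observed difference D and loss d per arm, the opposite-extreme difference is D(1 − d) − d.

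- It is zero at d = D/(1 + D) = 0.08/1.08 = 7.4%.
- At d = 15%, the sign is kept only if D exceeds 0.15/0.85 = 17.6 points.
- At d = 15% with 18% observed in the natural cycle, significance in favour of letrozole needs about 42.5% observed, a difference of 42.5 − 18 = 24.5 points.

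At 483 per arm with 26% and 18% observed:

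| Loss per arm | Lost | Letrozole | Natural cycle | Result |
|---|---|---|---|---|
| 2% | 10 | 123/483 | (85 + 10)/483 | p = 0.031, favours letrozole |
| 3% | 14 | 122/483 | (84 + 14)/483 | p = 0.066, favours letrozole |
| 8% | 39 | 115/483 | (80 + 39)/483 | RR 0.97, sign changed |
| 10% | 48 | 113/483 | (78 + 48)/483 | p = 0.33, sign changed |
| 15% | 72 | 107/483 | (74 + 72)/483 | p = 0.004, reversed |

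If the loss is counted as 483 − 420 = 63, the result is 109/483 = 22.6% versus (76 + 63)/483 = 28.8%, p about 0.03, still reversed.

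**5. What a graded analysis shows.** Use the same trial, with 72 lost per arm.

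- Lost letrozole women at 26%: the arm total is 107 + 0.26 × 72 = 125.7. The CI for the rate ratio first includes 1 when lost natural-cycle women have about 36% (26/72: 100/483, RR 1.26, CI 0.999 to 1.583).
- Lost letrozole women at 18%: the arm total is 107 + 0.18 × 72 = 120.0. The figure is about 29% (21/72: 95/483, RR 1.26, CI 0.995 to 1.602).

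A clinician can judge whether 36% or 29% is credible for lost natural-cycle women when 18% was observed. The contrast of 0% with 100% invites no such judgement.

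**6. Pilot scale.** With 50 per arm and 8 lost, 11/42 versus 8/42 gives p = 0.43. The worst case is 11/50 = 22% versus 16/50 = 32%, also reversed, but neither result is significant.

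**The case against.** The strongest reply is that the protocol does not prescribe the opposite-extreme rule. A reader might infer from the label that it does, and that the planned analysis will reverse a sound result. The text does not support this: the rule is undefined, and two of the alternatives in the working reverse nothing. This stands, and it makes the point conditional. It also shows why a definition is needed.

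A reader might also infer that the verdict is fixed by the loss rate whatever the data show. That goes too far. A large enough observed effect survives at 15% loss, the sign holds below 7.4%, and at 10% the reversal is not significant. The 15% is a sample-size allowance, not an observed rate.

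A third inference is that known outcomes of protocol violators will be overwritten. The protocol does not say so. The sentence may cover different analyses for different problems, and Step 2 sets intention to treat for all outcomes. What remains is an ambiguity to close.

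It is also fair that imputation is planned alongside, that a later SAP may supply all of this, that no decision depends on the sensitivity analysis, and that an extreme bound is meant to be pessimistic. These points limit the weight of the concern. They do not give the reader anything between the extremes, because the imputation commits to no range.

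**Conclusion.** The point holds in a conditional form. The worst-case analysis is undefined. Under its usual two-arm meaning, at the plan's own effect, loss and full sample size, it turns a significant benefit into a significant result the other way. Significance is lost by about 3% loss per arm and the sign changes above about 7.4%, roughly half the planned allowance. The bound alone is therefore uninformative about robustness at or near the planned loss and effect.

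This rests on the opposite-extreme reading, equal loss in both arms, observed rates equal to the planned rates, and 966 women; the statements about significance do not carry over to the 100-woman pilot. It is a change that should be made because it is cheap and improves what the trial can say. Confidence is moderate, because the scoring rule is assumed and the separate SAP is not available.

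**What to change.** In section 8, Step 3, or in the separate SAP before outcome data are seen:

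- State how a missing live-birth outcome is scored in each arm under the worst case and the best case, and present both as bounds.
- Supplement them with a pre-specified tipping-point analysis. Vary the live-birth rate of women with missing outcomes from 0 to 100%, separately in each arm. Report the combinations at which the 95% CI for the rate ratio includes 1. The worst and best cases are two corners of this grid, so nothing now planned is lost.
- State the imputation method and its assumption.
- State that this scoring applies only to missing outcomes. A woman with a protocol violation and a known outcome keeps that outcome, and any sensitivity analysis for violations is specified separately.

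The cost is about a paragraph of text, one extra table or plot, and slightly more explanation than a single number needs. Sample size, conduct and the primary analysis do not change.

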A distinction will be made between direct costs (costs like medical interventions and other healthcare costs like medical appliances) and indirect costs (costs of productivity loss or time loss costs). Costs will be measured in a subsample of participants.

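### The observed live-birth rates choose between cost-minimisation and cost-effectiveness analysis, with no margin or rule pre-specified for the equal effect that cost-minimisation presumes

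*Combined protocol and SAP*

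**What the plan says.** Section 8 (Economic evaluation) makes the type of analysis depend on the results: "Depending on the outcome of live birth rates in both groups, the economic analysis will be a cost-minimization of cost-effectiveness analysis". The sentence makes sense only if *of* is read as *or*. No criterion for the choice follows.

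The same subsection then lists outputs with no condition attached. "Cost-effectiveness of each strategy will be presented as cost per live birth" opens the list, which goes on to cost per clinical pregnancy. Sensitivity results are to be "expressed in ICER graphs and cost-effectiveness acceptability curves". It closes with "A decision model will be used to evaluate the optimal strategy".

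The rest of the plan asks a superiority question:

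- Section 2 tests whether letrozole increases live birth. It also names financial costs as one of three questions to answer.
- Section 4.4 sizes the trial to detect 26% against 18%, and calls 8 points the clinically relevant difference.
- Section 8, Step 2, plans a rate ratio with a 95% confidence interval and a test of difference ("A formal test of the difference in rate will be performed using chi-square test statistics"), with a log-rank test for live birth over time. It puts confidence intervals ahead of p-values.

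Section 8 also says "Details of the analysis will be described in a separate statistical analysis plan", to be finalised before data lock. It specifically assigns a stopping rule to that document, but no rule for the economic choice.

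**The concern.** Cost-minimisation is valid only where the two strategies can be taken as equally effective. A test of difference that fails to reach significance does not show that, and nothing else in the plan is set up to show it. With the trigger unstated, the natural fallback is to treat a non-significant live-birth result as equality. The economic report could then drop the effect side altogether while the data remained compatible with a gain that the protocol itself regards as clinically relevant.

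The list of outputs adds a second uncertainty. One analyst could attach cost per live birth, ICER graphs and acceptability curves to the cost-effectiveness branch only. Another could produce them in every case, which would leave the switch with little to do. Both would be following the text.

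What is at stake is the form and completeness of a secondary analysis, not the primary comparison.

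**Working it through.** **Inputs.** Section 4.4 gives 18% and 26%, two-sided alpha 0.05, power 0.80 (printed as beta), 15% loss and 483 per arm. Section 3 and section 4.4 also describe 100 women, that is, 50 per arm. The trigger is not in the documents, so two are assumed below.

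**1. The plan's own figure.** Pooled two-proportion formula, mean rate 0.22:

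n = [1.96 × √(2 × 0.22 × 0.78) + 0.8416 × √(0.18 × 0.82 + 0.26 × 0.74)]² / 0.08² = (1.148 + 0.491)² / 0.0064 = 419.7, so 420 per arm. Then 420 × 1.15 = 483. The stated size reproduces, and it is a superiority size.

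**2. Sizes used.** 483 per arm (everyone randomised, since "The analysis of all outcomes will be done on an intention to treat basis"), 420 (483 / 1.15), 411 (483 × 0.85) and 50.

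**3. Trigger A (assumed): a non-significant chi-square selects cost-minimisation.** Normal approximation with true rates of 18% and 26%:

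P(non-significant) = Φ{[1.96 × √(2 × 0.22 × 0.78 / n) − 0.08] / √[(0.18 × 0.82 + 0.26 × 0.74) / n]}

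- n = 483: Φ[(0.0522 − 0.08) / 0.0265] = Φ(−1.05) = 0.148
- n = 411: Φ[(0.0566 − 0.08) / 0.0288] = Φ(−0.81) = 0.208
- n = 50: Φ[(0.1624 − 0.08) / 0.0825] = Φ(1.00) = 0.841

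Exact binomial enumeration (chi-square without continuity correction) gives 0.146 at 483, 0.198 at 420, 0.207 at 411 and 0.837 at 50.

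**4. Trigger B (assumed): the 95% confidence interval for the difference lies wholly within ±8 points.** Same enumeration with Wald intervals.

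| True rates | Trigger A, 411 to 483 per arm | Trigger B, 411 to 483 per arm |
|---|---|---|
| 18% vs 26% | 20.7% to 14.6% | 2.5% |
| 18% vs 22% (assumed, half the relevant difference) | 70% to 66% | 29% to 34% |
| 18% vs 18% | 95% | 70% to 80% |

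Under trigger A with 18% vs 22%, 40% (411 per arm) to 31% (483 per arm) of all trials are non-significant with an interval that still reaches 8 points. Under trigger B that cannot happen, by construction.

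**5. Example.** 74/411 (18.0%) against 94/411 (22.9%):

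- Difference 4.9 points, standard error 2.81 points, 95% CI 4.87 ± 1.96 × 2.81 = −0.6 to 10.4, p = 0.08.
- Rate ratio 1.27, 95% CI 0.97 to 1.67, which includes 26/18 = 1.44.

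Trigger A would select a costs-only analysis here, although the interval includes the clinically relevant gain.

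**6. At 50 per arm.** With both arms at 18%, the half-width of the 95% CI is 1.96 × √(2 × 0.18 × 0.82 / 50) = 15.1 points. An interval this wide cannot lie within ±8 points, so at that size the plan's data could not support equal effect on an 8-point margin.

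**The case against.** Four points can fairly be made on the other side.

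**The plan is not without means.** A reader might infer that equal effect could never be shown. That goes too far. Section 8 plans 95% confidence intervals and section 4.4 supplies 8 points. If 8 points were pre-specified as a margin, the interval would fall inside it in 70% to 80% of full-size trials with equal rates (trigger B above). What is missing is the margin and the rule. At 50 per arm, however, the data could not do it either.

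**The list of outputs need not contradict the switch.** It can be read as describing the cost-effectiveness branch only, and a decision model could accompany either branch. This stands: the text is ambiguous, and a contradiction is not established.

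**The percentages depend on the trigger.** This also stands. Trigger A is an assumption, and it sits awkwardly with a plan that puts intervals above p-values. The 15% to 21% is in essence the type II error of a superiority trial planned for 80% power. Trigger B gives 2.5%.

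**The separate SAP could supply the rule.** It could, and the live-birth interval will be reported in either branch, so the uncertainty will not be hidden. But the result-dependent choice is already written into the protocol, and the SAP is not specifically assigned this rule.

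**Conclusion.** The point holds in a limited form. The protocol lets the observed live-birth rates select the type of economic analysis, and pre-specifies no margin or rule for the equality on which one of the two types depends. Which outputs go with which branch is unclear.

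The size is conditional. If non-significance were the trigger, a costs-only analysis would be chosen in about 15% to 21% of full-size trials with a true 8-point gain, and in about 84% with 50 per arm. With an interval-within-±8-points trigger, the full-size figure is about 2.5%. The documents name neither trigger, so these are illustrations of what the wording permits, not properties of the plan.

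A reader might also infer that the economic conclusion would be reversed. The documents give no costs, so that is not supported. The primary live-birth analysis is untouched. This is a minor correction to a secondary analysis, worth making because it costs almost nothing.

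**What to change.** Replace the result-dependent sentence in section 8 (Economic evaluation) with wording such as: *The cost-effectiveness analysis (incremental cost, incremental live births, ICER plane and acceptability curve, with joint uncertainty in costs and effects) will be reported whatever the live-birth result. Any comparison of costs alone will be labelled as supplementary.*

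This keeps the outputs already listed, removes the doubt about when they apply, and makes an equivalence margin unnecessary. Make the change before data lock.

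The cost is one sentence, with no data beyond those planned. The downside is that the ICER may be imprecise when the difference in live births is small. Showing incremental cost and incremental live births separately, with the plane and the curve, lets the reader see that imprecision.

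If the sponsor prefers to keep the switch, the minimum is a justified margin and an interval-based rule in the SAP. On an 8-point margin such a rule could work at full size but not with 100 women.

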9. ETHICAL CONSIDERATIONS

9.1 Regulation statement

The study will be conducted according to the principles of the Declaration of Helsinki (WORLD MEDICAL ASSOCIATION DECLARATION OF HELSINKI) Ethical Principles for Medical Research Involving Human Subjects Version Edinburgh, Scotland, October 2000, with Note of Clarification on Paragraph 29 added by the WMA General Assembly, Washington 2002 end Note of Clarification on Paragraph 30 added by the WMA General Assembly, Tokyo 2004 and in accordance with the Medical Research Involving Human Subjects Act (WMO) and other guidelines, regulations and Acts.

9.2 Recruitment and consent

Women eligible for participation in the study will be invited for additional counselling by a research nurse, to ensure that they are fully informed on the nature of the study by means of both oral and written information (Participant Information Form). Women who agree to participate will be asked to sign a written informed consent of which they will receive a copy.

9.3 Benefits and risks assessment, group relatedness

The strategies compared are already applied in current practice. No additional risks are expected. Women will not benefit by participating in this study, but the results

may prove beneficial for future couples who will undergo IUI.

10. ADMINISTRATIVE ASPECTS, MONITORING AND PUBLICATION

10.1 Handling and storage of data and documents

Data will be collected in a registration system. Data will be collected and entered in the system by local research nurses. Data monitoring will be done by principal investigators.

Data handling will be done anonymously, with the participant code only available to the local investigator and the research nurse working in the local centre. Participants will be asked for informed consent.

10.2 Amendments

Amendments are changes made to the research after a favourable opinion by the accredited METC has been given. All amendments will be notified to the METC that gave a favourable opinion.

A 'substantial amendment' is defined as an amendment to the terms of the METC application, or to the protocol or any other supporting documentation, that is likely to affect to a significant degree:

- the safety or physical or mental integrity of the subjects of the trial;
- the scientific value of the trial;
- the conduct or management of the trial; or
- the quality or safety of any intervention used in the trial.

All substantial amendments will be notified to the METC and to the competent authority.

Non-substantial amendments will not be notified to the accredited METC and the competent authority, but will be recorded and filed by the sponsor.

